9.3.2 Outcome Assessment

Primary outcomes

As primary outcomes the following data will be collected:

- characteristics of subjects with WT RAS non resectable mCRC receiving panitumumab in combination with chemotherapy as a 1st line treatment, including:
 - demographics: age, sex
 - targeted medical history: type of primary tumour and the date of diagnosis; site of primary tumour: rectum vs colon, right vs left colon; surgical procedures; lymph nodes: number and involvement; TNM stage; adjuvant chemotherapy, including regimen if applicable; sites of metastatic disease: liver, lung, other;
 - current status of mCRC: ECOG performance status, RECIST criteria (if available), ETS at week 8 (if available)
- pattern of treatment composed of:
 - 1st line treatment: agents and doses at baseline, any changes during
 1st line treatment, including dose, infusion schedule, and reasons for changes
 - 2nd line treatment: type of progression leading to 2nd line choice, type of 2nd line anti-cancer therapy, dose, schedule and reason for treatment selection

Secondary outcomes

In the secondary outcomes the following data will be gathered:

- Response to 1st line treatment measured as:
 - Death
 - Disease Progression
 - response rate (RR)
 - rate of conversion to resectable mCRC
 - tumour markers: CEA and CA 19.9
 - ETS (if available as per clinical practice) at week 8 measured by all or any of the following methods: CT, MRI, PET in comparison to the baseline.
- Safety assessments:
 - ADR reports related to panitumumab treatment
 - type and duration of ADR incident

Exploratory outcome

CCI

Date: 29 April 2019 Page 32 of 64

In study sites routinely performing biomarkers assessment in liquid biopsies, disease biomarkers information will be collected as per local regulations.

Since this is an observational study, all tests will be performed in line with routine clinical practice and no additional procedures are posed by the protocol.

9.3.3 Covariate Assessment

Certain pre-treatment factors (covariates) may be found to affect the pattern of treatment with panitumumab in combination with chemotherapy, therefore covariates will be investigated to evaluate their influence. However, subgroup analysis will be performed based on availability of data.

The following covariates may be analysed:

- Demographic: body weight, age, sex
- Location of primary tumour: colon (right or left) vs. rectum
- oxaliplatin-based chemotherapy for mCRC: yes vs. no
- irinotecan-based chemotherapy for mCRC: yes vs. no
- country
- total

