Panitumumab (Vectibix®) is a high-affinity (kd 5 x 10-11M), human immunoglobulin G2 (IgG2) monoclonal antibody directed against human EGFR (Davis, 1999; Yang, 1999). Panitumumab blocks the extracellular binding domain of EGFR that inhibits phosphorylation and activation of EGFR-associated kinases, such as epidermal growth factor (EGF), transforming growth factor-alpha (TGFα), and their ligands: amphiregulin, betacellulin, epiregulin, and heparin-binding EGF. The efficacy of panitumumab was similar to cetuximab (ASPECCT study; Price, 2014), but longer overall survival (OS) was observed in subjects treated with combination bevacizumab+panitumumab than bevacizumab+cetuximab (Price, 2016).

Therapeutic effect of panitumumab

The results of phase III study (PRIME) showed that panitumumab as 1st line treatment in combination with FOLFOX4 improved progression-free survival (PFS) of wild type (WT) *KRAS* subjects compared with FOLFOX4 alone (Douillard, 2010). Similarly, panitumumab+FOLFIRI vs. FOLFIRI monotherapy as 2nd line treatment resulted in improvements of PFS and OS (Peeters, 2015).

Panitumumab and bevacizumab were also compared in combination with FOLFOX as 1st line therapy PEAK - phase II study. Both treatments were associated with improved PFS, objective response rate (ORR), and resection rates, while OS was longer in the panitumumab+FOLFOX group (Schwartzberg, 2014).

Both PRIME and PEAK studies, highly evaluated on the Magnitude of Clinical Benefit Scale (MCBS) (Cherny, 2015), providing convincing evidence of the clinical validity of the high PFS and OS rates of panitumumab therapy.

RAS and BRAF gene analysis in CRC diagnostic

Mutations in *RAS* gene family: *KRAS* and *NRAS* predicted poor response to panitumumab+FOLFOX4 (Douillard, 2013) and to panitumumab+FOLFIRI (Peeters, 2015). Moreover, mutations in *BRAF* gene negatively predicted survival. Therefore, subjects with *BRAF* mutations are considered as high-risk regardless of other clinical parameters (Kohne, 2016).

The prevalence of *RAS* mutation was estimated at 43.6% (95% CI: 38.8-48.5%) based on 4,431 tumour samples (Kafatos, 2017).

Date: 29 April 2019 Page 18 of 64

RAS analysis is becoming routinely use based on the results of many studies, which support its predictive value (Rivera, 2017; Stintzing, 2016).

Early tumour shrinkage (ETS) as indicator of response to treatment

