It was shown that early, rapid and deep tumour shrinkage predicted delay in tumour progression and prolonged survival for a certain population of subjects. In the PRIME study more subjects with WT *RAS* mCRC receiving panitumumab+FOLFOX4 showed ETS than FOLFOX alone which was associated with longer PFS and OS (Douillard, 2015) and with improvement in quality of life in subjects with tumour symptoms (Siena, 2016). In the PEAK study, ETS was observed in more subjects treated with panitumumab+FOLFOX than bevacizumab+FOLFOX. A meta-analysis of pooled data from 3 panitumumab studies (PRIME, PEAK and PLANET) showed that ETS (≥ 20% or ≥ 30% at week 8) was associated with improvement in OS, PFS and resection rates in subjects with WT *RAS* mCRC (Rivera, 2015; Rivera, 2016).

Based on these results, new response-related outcomes, such as ETS and depth of response (DpR) were proposed as alternative to OS (Stintzing, 2016). ETS shown after a short period of treatment may provide an early measure of sensitivity to therapy in subjects with mCRC. Multiple studies indicated that ETS predicts PFS and OS independently of chemotherapy or targeted therapy used (Heinemann, 2015; Heinemann, 2016).

Location of tumour (left/right side of colon)

Another prognostic factor is the primary tumour location, ie, right versus left side of colon. Recently more studies investigated subjects with right-sided colon cancer (Saltzstein, 2007) connected with different epidemiology, clinical presentation, pathology, and genetic mutations comparing to subjects with left-sided colon cancer (Hansen, 2012).

A recent study reported an association between tumour location and survival (Rivera, 2017), indicating shorter survival of subjects with right-sided primary tumours when compared with left-sided primary tumours (Matos, 2016). However, there also is conflicting evidence, as, better survival of 91,416 subjects with right-sided stage I-III colon cancer versus 39,474 left-sided subjects was shown (Warschkow, 2016). Moreover, the lack of activity of anti-EGFRs in right-sided tumours was demonstrated in 75 RAS and BRAFWT subjects (Moretto, 2016), raising a question of optimal treatment choices.

Date: 29 April 2019 Page 19 of 64

In the light of inconsistent data, no consensus has been reached; therefore additional research is needed to understand the differences between right- and left-side colon cancer and their interaction with EGFR inhibition.

Adverse drug reaction (ADR): skin reactions

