 - evaluation and re evaluation / assessment (methods, criteria, timing Q2M), RECIST criteria (if available)
 - ETS at week 8 (if available, as per clinical practice) measured using all or any of the following methods: CT, MRI, PET
- Site characteristics.

Safety data will not be collected retrospectively, however side effects related to panitumumab treatment, and details of skin toxicity management will be collected as part of medical history.

Date: 29 April 2019 Page 28 of 64

The following key data will also be collected at Baseline where available. These data must originate from the time prior to the subjects' first dose of panitumumab in combination with chemotherapy:

 Method (incl. Brand name, if available) and date of RAS testing (test requested and result available), if available. Data on other biomarkers, if conducted, will also be collected.

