9.7.2 Planned Method of Analysis

9.7.2.1 General Considerations

The analysis of this study will be descriptive in nature. Counts and percentages will be provided for categorical outcomes. Continuous outcomes will be summarized by the number of non-missing values, mean, standard deviation, median, lower and upper quartiles and minimum and maximum values. Time to event data will be analysed using Kaplan Meier estimator.

For each outcome parameter, the covariates listed in Section 9.3.3 may be assessed in a logistic or general linear model overall for the selected European countries where data is appropriate. If available, non-significant factors will be eliminated stepwise until only covariates significant at the 5% level remain, thereby indicating which covariates have an important influence on treatment pattern. Summary statistics will then be reported for each level of the significant covariates and will be subject to local data availability.

Date: 29 April 2019 Page 36 of 64

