9.9.1.2 Confounding

Any confounding factors, such as demographic (eg, age, gender, country) or clinical characteristics (eg, primary tumour location, oxaliplatin-based chemotherapy for mCRC, irinotecan-based chemotherapy for mCRC) have been considered and the effort will be made to complement them during the study. For data analysis, the confounding factors will be controlled.

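### The covariate list omits baseline ECOG and BRAF status, so tumour-side comparisons are open to confounding that section 9.9.1.2 says will be controlled

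*Protocol*

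**What the plan says.** Section 9.3.3 introduces its list with "The following covariates may be analysed". The entries are body weight, age, sex, "Location of primary tumour: colon (right or left) vs. rectum", oxaliplatin-based chemotherapy (yes or no), irinotecan-based chemotherapy (yes or no), country and total. ECOG and BRAF are not among them.

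Section 9.7.2.1 says that, for each outcome parameter, these covariates "may be assessed in a logistic or general linear model overall for the selected European countries where data is appropriate", followed by stepwise removal of those not significant at 5%. Section 9.7.2.5.1 uses the same list for subgroups.

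Table 2 gives tumour location particular interest in relation to death, progression and ETS. Section 9.9.1.2 gives age, gender, country, tumour location and chemotherapy type as examples of confounders and states: "For data analysis, the confounding factors will be controlled".

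On the two missing factors:

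- **BRAF.** Section 7.1 says BRAF mutation negatively predicted survival and that subjects with BRAF "mutations are considered as high-risk regardless of other clinical parameters". It describes right-sided disease as "connected with different epidemiology, clinical presentation, pathology, and genetic mutations comparing to subjects with left-sided colon cancer". Section 9.2.5 does not name BRAF as a data item; it says only: "Data on other biomarkers, if conducted, will also be collected". Section 9.9.3 acknowledges limited availability of biomarker data.
- **ECOG.** It is collected at baseline and monthly (sections 9.2.5 and 9.2.6, Appendix E). In section 9.3.2 it is part of the current status of mCRC, together with RECIST criteria and week-8 ETS where available.

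**The concern.** Tumour side is the subject characteristic the protocol singles out, and section 7.1 presents the interaction of side with EGFR inhibition as unresolved. A right-versus-left difference in death or progression will attract attention even in a descriptive report. If a strong prognostic factor is unevenly distributed between the sides and is not adjusted for, part of any difference belongs to that factor.

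The protocol's own background points to BRAF as a candidate, and performance status is an obvious baseline item to adjust for because it is already collected. Neither can enter a model built from section 9.3.3, so the general promise in section 9.9.1.2 cannot be met for them.

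**Working it through.** **1. The plan's own figure.** The protocol gives no figure for a tumour-side contrast. Its one precision figure is a 95% confidence half-width of at most 4 percentage points with 600 subjects (Abstract, Study Sample Size). Check at a proportion of 0.5: 1.96 × √(0.25/600) = 0.0400, or 4.00 points (3.99 by the Wilson method). It reproduces, and adding covariates does not alter it.

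**2. What the text establishes for each factor.**

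| Question | BRAF | Baseline ECOG |
|---|---|---|
| Called prognostic in the protocol? | Yes, section 7.1 | Not stated |
| Said to differ by tumour side? | Not by name; section 7.1 says only that mutations differ | No |
| Collected? | Only as another biomarker, if tested (9.2.5) | Yes, where recorded (9.2.5, Appendix E) |
| On the list in 9.3.3? | No | No |
| Among the examples in 9.9.1.2? | No | No |

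**3. How large the distortion could be.** Every input in this step is an assumption, because the protocol gives neither prevalence by side nor a hazard ratio. For a binary factor with hazard ratio HR and prevalence pR (right) and pL (left), and no true side effect, the apparent right-versus-left hazard ratio is approximately

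B = [1 + pR(HR − 1)] / [1 + pL(HR − 1)].

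This uses prevalences at the start of follow-up, so it is a guide and not an exact value.

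BRAF, with pL = 5%:

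| HR | pR = 5% | pR = 10% | pR = 20% | pR = 30% |
|---|---|---|---|---|
| 1.5 | 1.00 | 1.02 | 1.07 | 1.12 |
| 2 | 1.00 | 1.05 | 1.14 | 1.24 |
| 3 | 1.00 | 1.09 | 1.27 | 1.45 |

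Examples: at HR 2 and pR 20%, B = 1.20/1.05 = 1.14. At HR 3 and pR 30%, B = 1.60/1.10 = 1.45.

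ECOG 2 or more, with pL = 10%, pR = 10% to 20% and HR 1.5 to 3: B runs from 1.00 to 1.40/1.20 = 1.17.

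**4. The same question on the odds-ratio scale**, which suits the logistic model in section 9.7.2.1. Assume BRAF mutation in 15% to 30% (right) and 5% (left), an odds ratio of 2 to 4, and a risk in wild-type subjects of 30% to 50%.

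- Upper end (30% right, odds ratio 4, risk 30%): the risk in mutated subjects is 1.714/2.714 = 0.632. Right: 0.30 × 0.632 + 0.70 × 0.30 = 0.399. Left: 0.05 × 0.632 + 0.95 × 0.30 = 0.317. Crude odds ratio 1.44.
- Lower end (15% right, odds ratio 2, risk 50%): risks 0.525 and 0.508. Crude odds ratio 1.07.

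This range stays above 1.00 only because equal prevalence was not among its inputs.

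**5. Precision in a BRAF-tested subset.** If 30%, 50% or 80% of 600 were tested (180, 300 or 480 subjects; assumed shares), the worst-case half-width for a proportion would be 7.3, 5.7 or 4.5 points, against 4.0 for all 600. The known wild-type group would be somewhat smaller again.

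**The case against.** The strongest reply is that the protocol fixes no adjusted tumour-side analysis that could fail. The study is descriptive with no hypothesis, death and progression are analysed by Kaplan-Meier, and the models are optional. Section 9.3.3 gives its reason as factors that "may be found to affect the pattern of treatment with panitumumab in combination with chemotherapy", not factors for survival. Further detail is left to the SAP (section 9.7.1), and the confounders in section 9.9.1.2 are only examples. BRAF is often unavailable, and section 9.9.3 says so.

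Much of this stands, and it limits the point. It does not remove it: section 9.7.2.1 extends the list to each outcome parameter, the protocol states the list itself, and the sentence on control of confounding carries no condition.

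Three stronger readings are tempting and are not supported:

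- **That the tumour-side result is confounded.** No section says BRAF or ECOG differs by side, and at equal prevalence the bias is nil. Section 7.1 also cites lack of anti-EGFR activity in right-sided tumours among 75 RAS and BRAF wild-type subjects, so its background does not reduce the side question to BRAF.
- **That BRAF is collected at baseline.** It is not a named item and enters only where testing was done.
- **That ECOG is ignored.** Current disease status, which includes ECOG, is an exposure variable for the response outcomes in Table 2 and a descriptive breakdown in section 9.7.2.4. However, the sentence in 9.7.2.4 covers response rate, tumour markers and later treatment, not death or progression. A composite that also holds week-8 ETS cannot stand in for ECOG at first dose, and a separate breakdown does not adjust the side comparison.

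**Conclusion.** The point holds in a limited form. The list omits one baseline factor that is collected and one that the protocol itself calls high-risk and may hold for some subjects. Tumour-side comparisons built from that list, or left unadjusted, are open to confounding, and section 9.9.1.2 promises more than the list can deliver.

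Under the stated assumptions a null side effect could appear as a hazard ratio of 1.00 to 1.45 through BRAF and 1.00 to 1.17 through ECOG. These are illustrations, not estimates. The existence and size of any bias turn on imbalances between sides that the protocol does not report. No power or sample-size statement is affected. The change should be made because it is cheap and the affected comparison is one the study singles out.

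**What to change.** 1. Add baseline ECOG, dated to first dose, to section 9.3.3. Keep it together with tumour location in any model of death, progression, response or ETS on tumour location, exempt from the 5% stepwise elimination in section 9.7.2.1.
2. Name BRAF status in section 9.2.5 as an item to record where already tested. Report the number tested by side, and repeat the side result among subjects known to be BRAF wild type as a sensitivity analysis. Restriction is preferable to adjusting with a not-tested category, which can itself bias the side estimate when testing depends on the centre.
3. Label any side result without this adjustment as unadjusted description, and limit the sentence in section 9.9.1.2 to the factors actually adjusted for.

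The cost is a few lines in sections 9.2.5, 9.3.3, 9.7.2.1 and 9.9.1.2, a BRAF field in the eCRF if none exists, and one extra table. No new test or procedure is needed. The BRAF check will be partial and less precise, because status will be known only in a subset.

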9.3.4 Validity and Reliability

To ensure that observations will be consistent across time and sites, the eCRF will be developed to only abstract data as documented in the medical record. During data abstraction the emphasis will be put on objectivity and lack of data interpretation. To determine the reliability of data, measures of quality will be frequently performed on data transfers during the study period.

The observation instruments used in the study, like RECIST and ECOG are validated, acceptable and have been shown in cancer trials to be sensitive to change.

The Investigator and/or designee will be involved in validation of the data recording activities.

Amgen will define critical data and will control the data lifecycle to assure data integrity. Data lifecycle validation will include data creation and capture, data processing, review,

Date: 29 April 2019 Page 33 of 64

reporting (incl. handling of invalid and atypical data), data retention and retrieval. Amgen will prepare adequate training and procedures (SOPs) that will provide users the ability to review the existing data source, such as electronic health records and process the data in an effective and efficient process.

9.4 Data Sources

Retrospective data will be retrieved from medical files and will include subject's medical records from Baseline (the date of the start of panitumumab in combination with chemotherapy) to enrolment (the date of signing ICF).

During the study, data will be collected by the treating physician during subject's routine clinic visits. Data will be coded using the latest version of the medical dictionary for regulatory activities (MedDRA). Data will be validated using the electronic CRF.

In countries where the use of the FACT-EGFR1-18 (See Appendix F) questionnaire is allowed per local regulations and local language is available, additional data will be collected from subjects by means of a paper questionnaire.

9.5 Study Size

This study will enrol approximately 600 subjects in total with initially non resectable wild type *RAS* mCRC receiving panitumumab in combination with chemotherapy as 1st line treatment.

The sample size will provide reasonable precision to enable statistical analysis as described in Section 9.6 The size of the subject population will fulfil the requirements of reimbursement agencies in the selected European countries.

9.6 Data Management

Data are abstracted by site staff from subject medical files into an electronic database provided by the sponsor. The sponsor provides protocol-specific training to all site staff delegated to abstract subject data. An eCRF Completion Guideline will be provided.

The Amgen representative(s) and regulatory authority inspectors are responsible for contacting and visiting the Investigator for the purpose of inspecting the facilities and, upon request, inspecting the various records of the clinical study (eg, eCRFs and other pertinent data) provided that subject confidentiality is respected.

The Clinical Monitor or designee is responsible for verifying the eCRFs at regular intervals throughout the study to verify adherence to the protocol completeness, accuracy, and consistency of the data; and adherence to local regulations on the conduct of research. The Clinical Monitor, or designee is to have access to subject

Date: 29 April 2019 Page 34 of 64

medical records and other study-related records needed to verify the entries on the eCRFs in accordance with the local laws and regulations.

The Investigator agrees to cooperate with the Clinical Monitor, or designee to ensure that any problems detected in the course of these monitoring visits, including delays in completing eCRFs, are resolved.

In accordance with the sponsor's audit plans, this study may be selected for audit by representatives from Amgen's Global Compliance Auditing function (or designees). Review of study-related records will occur to evaluate the study conduct and compliance with the protocol, and applicable regulatory requirements.

Data capture for this study is planned to be electronic and via a paper questionnaire (in countries where FACT- EGFRI-18 QoL questionnaire (See Appendix F) use is permitted):

- All source documentation supporting entries into the electronic eCRFs must be maintained and available upon request.
- Updates to electronic eCRFs will be automatically documented through the software's "audit trail". The data from the paper questionnaire (See Appendix F) will be entered by site staff into the electronic data capture (EDC) system database
- To ensure the quality of clinical data across all subjects and sites, a clinical data management review is performed on subject data received at Amgen. During this review, subject data is checked for consistency, omissions, and any apparent discrepancies. In addition, the data will be reviewed for adherence to the protocol and ICH GCP. To resolve any questions arising from the clinical data management review process, data queries and/or site notifications are created in the EDC system database for site resolution and closed by an Amgen reviewer.
- The Investigator signs only the Investigator Verification Form for this electronic data capture study. This signature indicates that the Investigator inspected or reviewed the data on the CRF, the data queries, and site notifications, and agrees with the content.

